The preoperative and postoperative care for these patients is standardized. The surgical procedure is minimally invasive, performed through 3-4 small incisions, usually no larger than 3cm each. The hospital inpatient recovery is typically for 3-5 days, with regular scheduled postoperative visits at 2-3, 6-7 weeks, and 12-14 weeks from surgery. The timing of this first visit is specified so that a decision can be made as to whether the patient can proceed with additional treatment, such as radiation to the operated extremity, or chemotherapy. The key parts of this assessment include inspecting the surgical wounds for signs of infection and assessing the adequacy of soft tissue healing. In addition, the radiographic studies (x-rays) of the extremity are viewed by the physician. The time required for a surgeon to make this assessment for uncomplicated cases is typically short, averaging 5-7 minutes.

The post-operative follow-up visit utilizes standardized tools to establish patient-centered outcome data with a direct impact on the individual survivor as well as contributing to a dataset for predicting functional outcomes for all bone cancer survivors. However, only one-third of those seen are from local areas, and surveillance of persistent, late effects following surgery is suboptimal. Numerous obstacles limit both the patients' ability to attend face-to-face appointments (cost of travel, impaired mobility), and the providers' ability to collect patient-centered outcome data (clinic capacity). At our clinic, data show that approximately 30% of our patients miss an appointment in the post-operative period. A missed follow-up appointment prevents medical intervention needed to enhance survivorship and reduces data collection, which in turn, makes it difficult to accurately predict outcomes over time for future bone cancer survivors.

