The use of mobile devices has the potential to improve the delivery of cost-effective, high-quality, standardized surveillance of cancer survivors. In contrast to other medical subspecialties, long-term survivorship research on post-surgical patients using mobile devices has been uncommon. This study proposes to develop and test a novel web-based mobile technology for surveillance of cancer survivors following surgery for bone metastases. The study will focus on three aspects of feasibility of the proposed new approach: adaptation, limited efficacy testing, and acceptability.⁸⁴ The potential economic impact includes cost savings for both patients and providers. The potential impact on survivorship care is to optimize the frequency and fidelity of outcomes research needed for the aging cancer survivor following skeletal surgery.¹⁸

The optimal surveillance system that preserves patient privacy, preserves overall fidelity, minimizes cost, and allows for requisite data quality has not yet been identified [5, 16, and 17]. In this

PI: [name], PhD

Protocol: 2015-0966

August 21, 2018

study, we propose to use mobile devices to enhance the regular postoperative surveillance of cancer patients, all of whom have undergone intramedullary fixation for cancer metastases in the bone.

3.0 Patient Eligibility:

Patients will be eligible to participate in this study if they:

- Have been scheduled for an Intramedullary nailing (IM) surgery with the department of Orthopaedic Oncology at UT MD Anderson Cancer Center.
- Are able to read and write English.
- Are 18 years or older.
- Are willing and able to use a smartphone or tablet comfortably.
- Have access to mobile hot spot, wireless internet, and/or cellular service.
- Must have a caregiver or assistance at home who can assist with collecting PT measures.

Exclusion Criteria:

- None

4.0 Research Plan and Methods:

The objectives for this protocol will be achieved in multiple steps to ensure patient safety. There are six outcome measures, including one that is completed by the patient, two by the clinician, and three assessed by the physical therapist (see **Outcomes** section below).

Outcomes

Functional outcomes and quality of life will be assessed in this study via the following instruments:

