1. The National Institute of Health Patient Reported Outcomes Measurement Information System for General Health (NIH PROMIS GH)⁸⁷ is a validated instrument widely used to assess patients' perceptions of their quality of life. The NIH PROMIS GH is completed by the patient and is composed of eight parameters that include physical functioning, physical role, bodily pain, general health perceptions, vitality, social functioning, emotional role and mental health. The physical function item bank measures self-reported capability rather than actual performance of physical activities. This includes the functioning of one's upper extremities (dexterity), lower extremities (walking or mobility), as well as instrumental activities of daily living, such as running errands. (Appendix G)
2. The Musculoskeletal Tumor Society functional score (MSTS)²⁸ is a validated instrument completed by the clinician to objectively evaluate the functional outcome of patients treated with surgery for the management of tumors of the musculoskeletal system in either the upper or lower extremity. The MSTS assigns numerical values (0-5) to six categories: in the lower extremity, pain, function, emotional acceptance, supports, walking ability, and gait pattern; and in the upper extremity, pain, function, emotional acceptance, hand positioning, manual dexterity, and lifting ability. Normal function corresponds to a score of 30. (Appendix C)

3. The Eastern Cooperative Oncology Group score (ECOG)⁽²²⁾ is a clinician-scored indicator of the cancer survivor's general function using categorical grades as follows: (0) fully active at pre-disease performance without restriction, (1) ambulatory and able to carry out light, non-strenuous work, (2) ambulatory, capable of self-care, up and about more than 50% of waking hours, (3) capable of limited self-care, confined to a chair or bed more than 50% of waking hours, (4) cannot perform self-care, totally confined to chair or bed, and (5) dead. (Appendix D)

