Once the adaptation of the face-to-face follow-up to the mobile format has been verified, we will move to the limited efficacy testing (Objective 2/Specific Aim 3). A group of 40 patients that fit the inclusion criteria and have completed the informed consent process will be enrolled in the study. Participants will be enrolled in either a control group (n=20) or to the mobile surveillance group (n=20). The control group will have face-to-face follow up visits with no mobile surveillance at the appropriate time points. The mobile surveillance group (n=20) will have both face-to-face visits and additional data obtained using mobile devices. Patients in both groups will complete the same set of outcome measures. These measures will be administered at the following time points, 2, 6, 12, and 24 weeks.

Patients in the mobile surveillance group will complete an assessment using a mobile device at home during the week after their scheduled clinic visit at 2, 6, 12 and 24 weeks (see **Table 1** below). The mobile device data is in addition to data gathered at face-to-face clinical appointments, thereby adding outcome data and enhancing surveillance overall. Participants in the mobile surveillance group will take videos using the mobile devices and upload the data over the encrypted network using the My MD Anderson secure email transmission. Participants will be provided with a mobile device (or tablet) that is enabled with a mobile hot spot for data transmission. For recovery of function, video sequences will be acquired by patients performing prescribed tasks that will be used to quantify functional status according to the MSTS, ECOG, TUG, EVGS, FSST, NIH PROMIS GH Score. The participant's surgical wound will also be photographed using the mobile device. Quality of Life questionnaires and PROMIS SF v1 (Appendix G) surveys will be sent to the group for completion on their mobile device via REDCap Software or thru My MD Anderson email.

To ensure patient safety, participants in the mobile surveillance group will also engage in videoconferences at the prescribed timepoints using Vidyo or Zoom. All patient communication will be documented as follow-up notes in Clinic Station by the clinician.

Table 1. Study Design

Control Group n = 20	Mobile Surveillance Group Patients n = 20
Postoperative clinic visits	Postoperative clinic visits
2 weeks	2 weeks
6 weeks	6 weeks
12 weeks	12 weeks
24 weeks	24 weeks
Measures:	Measures:
Completion rates	Completion rates

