There are two measurements for limited efficacy testing, completion rate and patient satisfaction/acceptability. Among the set of questionnaires the patients need to complete, MSTS,

PI: [name], PhD

Protocol: 2015-0966

August 21, 2018

TUG, and PROMIS are considered the most important. A patient is considered having completed the follow-up assessment if the three outcomes are documented for the 2-, 6-, 12, and 24-week evaluations. We will then report the completion rates for each group for comparison.

We will report the patient satisfaction rate using patient satisfaction surveys for both the control and the study groups. When the sample size is 20, a two-sided 95% confidence interval (CI) for completion rate or satisfaction rate using the large sample normal approximation will extend at most 0.22 from the observed rate (nQuery Advisor 7.0). When the sample size in the group is 20, the 95% CI will extend 0.30 from the observed difference in rate assuming the rate is 0.50 for one group and 0.70 for the other group. The physician satisfaction rate for using mobile devices will be reported. We will also address the economic impact for using mobile devices. Repeated measures analysis may be utilized to evaluate change over time in the completion status or questionnaire scores for each method.

7.0 Data Management and Security:

All patient-reported and task performance outcomes and clinical data (including videos/photos) gathered under this protocol will be stored in a password-protected database. Data will not be transferred to laptop computers that are removed from the institution. Identifiers (name, medical record number) will be collected but will be replaced by study numbers in the analytic file. The key linking these numbers will be retained in a locked file by the investigator.

Data (including videos/photos) using mobile devices or tables will be encrypted by the IT department securely transferred using MY MD Anderson secure email to the research team.

Only MDACC personnel designated by the Principal investigator will have access to study records/data. These personnel will be fully trained to maintain the confidential nature of the patient health information. Paper records will be stored in locked files inside a locked office. External storage will be password protected.

Study data will not be shared with any individuals or entities that are not involved in the study. These data will be used only for research purposes and for this research study.

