8.0 Human Subjects Protection:

Collection of Identifiers: Identifiers (including name, medical record number and basic information, such as demographics, type of cancer and surgical procedure) will be collected by MDACC study personnel designated by the Principal Investigator, but will be replaced by study numbers in the analytic file. This information is already documented and available in the routine medical record. The key linking these numbers and all study data will be stored on password-protected computers. Study-related documents will be retained by designated study staff in locked files. Participant-identifying information will be kept confidential and will be available only to the PI and relevant study staff who have been trained to maintain patient health information.

Training of Personnel: Only MDACC personnel designated by the Principal Investigator will have access to study records. These personnel will be fully trained to maintain the confidential nature of the patient health information. All of the study personnel have completed the institution's research and human subjects training.

Data Sharing: Study data will not be shared with any individuals or entities that are not involved in the study.

9.0 Reporting of Adverse Events:

This PI initiated study is a low-risk study. The participants in both groups will continue to have regular follow-up appointments as scheduled.

The following adverse events will be tracked by the PI:

PI: [name], PhD

Protocol: 2015-0966

August 21, 2018

- Possible postoperative complications including wound infection, wound dehiscence, thromboembolism, and hardware failure/breakage. Adverse events and complications detected via mobile device will be addressed by instructing the patients to be seen in the emergency room or clinic. In case the participant does not submit a video or pictures at the appropriate timepoints, the study coordinator will contact the participant by phone and assess for the above adverse events.
- In the event that a patient may experience an adverse event during evaluation using a mobile device (i.e. falls while performing physical therapy assessments), he/she will be directed to call 911 or present to the local hospital for treatment. The treating surgeon will be notified.

9.0 References:

1. Hortobagyi, G. N. (2007). A shortage of oncologists? The American Society of Clinical Oncology workforce study. *Journal of Clinical Oncology*, 25(12), 1468-1469. doi: 10.1200/JCO.2007.10.9397

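### The completion rate in Section 6.0 counts a patient who dies before week 24 as a non-completer, so the group comparison mixes survival with follow-up performance

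*Combined protocol and SAP*

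**What the plan says.** Section 6.0 (Limited Efficacy Testing) names two measures, completion rate and patient satisfaction. It singles out MSTS, TUG and PROMIS as the outcomes that matter most, and then defines completion per patient: "A patient is considered having completed the follow-up assessment if the three outcomes are documented for the 2-, 6-, 12, and 24-week evaluations". The rates are to be reported by group and compared. The precision statement uses 20 per group, and for the difference it works "assuming the rate is 0.50 for one group and 0.70 for the other group". An optional analysis follows: "Repeated measures analysis may be utilized to evaluate change over time in the completion status".

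Other places that bear on the point:

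- Section 2.0 describes the patients as "all of whom have undergone intramedullary fixation for cancer metastases in the bone". Section 3.0 sets no life-expectancy criterion and lists no exclusions.
- Section 2.0 gives the problem that the programme is meant to address: "At our clinic, data show that approximately 30% of our patients miss an appointment in the post-operative period".
- Section 4.0 (Outcomes) lists the top ECOG grades as "cannot perform self-care, totally confined to chair or bed, and (5) dead". This is the only place where death appears as a patient state, and ECOG is not one of the three completion outcomes.
- Section 4.0 (Specific Aim 3) places 20 patients in each group without saying how they are allocated. Follow-up ends at 24 weeks.
- Section 9.0 (Reporting of Adverse Events): "In case the participant does not submit a video or pictures at the appropriate timepoints, the study coordinator will contact the participant by phone". The call checks for listed complications, and death is not among them.

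**The concern.** The definition requires all four evaluations. A patient who attends weeks 2, 6 and 12 and dies at week 20 has missed nothing that was due, yet is classified with a patient who never came back. No section states how a death is handled, and the optional repeated-measures analysis has no rule for evaluations that fall after death.

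In a cohort with metastatic bone disease followed for 24 weeks, deaths are foreseeable. The study's stated problem is missed appointments, and completion is one of only two limited-efficacy measures. A rate that includes deaths cannot be read on its own as how well follow-up was carried out. If deaths differ between the groups, the reported difference moves even when follow-up of living patients is identical. Because no allocation method is described, similar mortality in the two groups cannot be taken for granted.

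**Working it through.** **Inputs from the documents.** 20 patients per group; evaluations at weeks 2, 6, 12 and 24; planning rates 0.50 and 0.70; stated half-widths of at most 0.22 (single rate) and 0.30 (difference), all from Section 6.0.

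**Assumed inputs.** The documents give no mortality, so 24-week mortality m is taken from 10% to 40%. Completion among survivors, c, is set at 0.70 for illustration.

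**1. The plan's own figures.**

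- Single rate, worst case: 1.96 × √(0.50 × 0.50 / 20) = 0.219, stated as 0.22.
- Difference: 1.96 × √((0.50 × 0.50 + 0.70 × 0.30) / 20) = 0.297, stated as 0.30.

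Both reproduce with all 20 patients per group in the denominator.

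**2. What the rate measures.** With all enrolled patients as denominator, a completer must be alive at week 24, so rate = (1 − m) × c.

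| m | highest attainable rate (c = 1) | rate if c = 0.70 |
|---|---|---|
| 0.10 | 0.90 | 0.63 |
| 0.20 | 0.80 | 0.56 |
| 0.30 | 0.70 | 0.49 |
| 0.40 | 0.60 | 0.42 |

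**3. Unequal deaths, identical follow-up.** With d deaths in a group and c = 0.70, the rate is 0.70 × (20 − d) / 20, so each death moves it by 0.70 / 20 = 0.035.

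- d = 2: 0.70 × 18 / 20 = 0.63.
- d = 6: 0.70 × 14 / 20 = 0.49.
- Gap: 4 × 0.035 = 0.14.

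If misses are independent of each other and of death, the rate among evaluations due while alive is 0.70^(1/4) = 0.915 in both groups, so that rate shows no gap.

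**4. How easily death counts differ.** With equal true mortality of 10, 20, 30 or 40% and two binomial samples of 20, the chance that the counts differ by 3 or more is 0.18, 0.32, 0.39 or 0.42. Three deaths move the difference by 3 × 0.035 = 0.105. This part is sampling variation, which the confidence interval for the all-enrolled rate already covers. A systematic difference in mortality would not be covered.

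**5. Effect on stated precision.** Replace the planning rates by 0.50(1 − m) and 0.70(1 − m). At m = 0.20 they are 0.40 and 0.56, and 1.96 × √((0.40 × 0.60 + 0.56 × 0.44) / 20) = 0.306. At m = 0.10, 0.30 and 0.40 the half-width is 0.304, 0.303 and 0.295. All are close to 0.30.

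**6. Precision of a per-evaluation rate.** Take 80 evaluations per group (20 × 4), choose per-evaluation rates that reproduce all-four rates of 0.50 and 0.70, and use half-width = 1.96 × √((1 + 3ρ) × (p₁(1 − p₁) + p₂(1 − p₂)) / 80), where ρ is the intra-patient correlation. The matched rates change with ρ.

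- ρ = 0: rates 0.841 and 0.915 (fourth roots); half-width 0.10.
- ρ = 0.5 (beta-binomial match): rates about 0.70 and 0.84; half-width 0.20.
- ρ = 1: rates 0.50 and 0.70; half-width 0.30.

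Removing evaluations after death, with constant hazard, leaves 80 × the mean of (1 − m)^(t/24) over t = 2, 6, 12, 24, which is 76.3 to 64.3 evaluations for m from 0.10 to 0.40. This widens the intervals slightly.

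**The case against.** The best case on the other side has five parts.

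- **The denominator is implied.** Attaching 20 per group to the completion-rate interval points to all enrolled patients. This stands: a reader might infer that the measure has no usable denominator, and the documents do not support going that far. But 20 is a planning figure, and the all-enrolled reading is the one under which deaths become non-completion.
- **The stakes are low.** This is a descriptive pilot, and its only progression rule is MSTS agreement in the feasibility step. This stands. The illustrative gap of 0.14 also lies well inside the plan's own half-width of 0.30.
- **The sizes are assumed.** This stands too. Mortality, 0.70 among survivors and the 2 v 6 split are not in the documents. A reader might also infer that the planned difference of 0.20 shrinks. That follows only if 0.50 and 0.70 are rates among survivors. Section 6.0 uses them only as inputs to precision, and if they already include deaths nothing shrinks.
- **A while-alive rate still mixes in illness.** TUG requires standing and walking, so a patient alive but too ill to do it counts as non-complete. This is right and limits what the added rate can show.
- **The safety call is weak evidence about data collection.** Section 7.0 describes systems, not a list of fields, so it cannot be inferred that dates of death or reasons for missing will go uncollected. What can be said is that the plan does not ask for them. In the 20 v 20 phase the call would reach only the mobile group, since only that group submits videos and pictures.

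The optional repeated-measures analysis does not answer the point: it may not be run, and its per-evaluation status is not defined.

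**Conclusion.** The concern holds as a matter of interpretation. Applied as written to the 20 enrolled per group, the definition makes the compared rate a product of survival and completion among survivors, and nothing elsewhere in the documents separates the two. That conclusion follows from the definition and needs no mortality assumption. The size does: 0.035 per extra death, and 0.63 v 0.49 at 2 v 6 deaths, rest on 0.70 completion among survivors in both groups and on death counts chosen for illustration.

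A reader might go on to conclude that the precision statement is wrong or that a decision rule is compromised. Neither follows. Both half-widths reproduce and hardly change when deaths are included, and no test or go/no-go rule depends on completion. This is a gap that should be fixed because it affects one of two limited-efficacy measures and the repair is cheap; it does not invalidate the pilot.

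**What to change.** In Section 6.0:

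1. State that the all-four completion rate is over all 20 enrolled per group and that death before week 24 counts as non-completion.
2. Report beside it a per-evaluation rate: evaluations with MSTS, TUG and PROMIS all documented, divided by evaluations due while the patient was alive. No-shows and withdrawals count as non-completion. Use a confidence interval that allows for clustering by patient.
3. Report the number of deaths in each group.
4. Record the date of death and the reason for each missing evaluation, in both groups.

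**Cost.** A few sentences, one further reported rate and two data items. Sample size is unchanged, and the existing precision statement can stay for the all-four rate. The added rate should not be promised as more precise: depending on how strongly misses cluster within patients, its half-width for the difference runs from about 0.10 to 0.30 before evaluations after death are removed.

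**Downside.** The added rate conditions on survival, which is why the all-enrolled rate is kept. It also still counts living patients too ill for the TUG as non-complete; the recorded reasons help to show how many there are.

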MSTS, TUG, ECOG, EVGS, FSST, NIH PROMIS GH	MSTS, TUG, ECOG, EVGS, FSST, NIH PROMIS GH
	Mobile device surveillance follow up (in week after clinic visit) 2-3 weeks 6-7 weeks 12-13 weeks 24-25 weeks Measures: Completion rates MSTS, TUG, ECOG, EVGS, FSST, NIH PROMIS GH + wound image + videoconference with physician to ensure safety

Specific Aim 4: Acceptability

To assess acceptability of the mobile format by patients and physicians (Objective 3/Specific Aim 4), the data collected will be used to assess:

- Patient acceptance of mobile device surveillance for data collection.
- Clinician acceptance of data collection using mobile device surveillance.
- Ability to detect relevant outcome measures, wound complication, and/or adverse postoperative.

Patients will be included in the study until 24 weeks (6 months) after surgery. Upon completion of the study, both groups of participants will complete a survey evaluating satisfaction with care and the use of the mobile devices (Appendix J). In addition, clinicians from within the department of Orthopaedic Oncology will be recruited and asked to participate in this protocol. Surgeons, physician assistants and physical therapists that have agreed to and have participated in the telemonitoring program will complete surveys (Appendix I) created by the Orthopaedic Research

PI: [name], PhD

Protocol: 2015-0966

August 21, 2018

Team. Approximately, 12 clinicians will be participating in this study. These surveys were created by the research team and were adapted from a validated survey, the RAND Health Patient Satisfaction Questionnaire (PSQ). This was originally developed by Ware, et. al.(Ware, Snyder, and Wright, 1976). PSQ-18 is a short form version that retains many characteristics of its full-length counterpart. The satisfaction surveys used for this study were modified from PSQ-18.

5.0 Informed Consent:

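### Patient satisfaction is analysed only as a rate with no stated cut; if the survey yields a score, adding a score comparison would usually give a tighter answer from the same 40 patients

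*Combined protocol and SAP*

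**What the plan says.** Section 6.0, Limited Efficacy Testing, opens: "There are two measurements for limited efficacy testing, completion rate and patient satisfaction/acceptability". For satisfaction it then says: "We will report the patient satisfaction rate using patient satisfaction surveys for both the control and the study groups". The precision statements in that section are all for rates. One group of 20 is given a half-width of at most 0.22, and for two groups "the 95% CI will extend 0.30 from the observed difference in rate assuming the rate is 0.50 for one group and 0.70 for the other". Clinicians are treated alike: "The physician satisfaction rate for using mobile devices will be reported".

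Section 4.0, Specific Aim 4, describes the instrument: "The satisfaction surveys used for this study were modified from PSQ-18". It is completed once, when the study ends, by patients in both groups, and covers both their care and the devices.

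The text supplied has no rule for calling a patient satisfied, no reason for using a rate, and no analysis of a satisfaction score. Section 6.0 does allow an optional repeated measures analysis of questionnaire scores, but that concerns change over time and cannot apply to a survey given once.

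**The concern.** Two things follow if the survey gives more than a yes/no answer.

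- **Precision.** Turning a graded score into satisfied or not satisfied treats a patient just above the cut and one far above it as the same. With 20 per group the plan already accepts an interval of ±0.30 on the difference in rates, so there is little precision to spare.
- **An open definition.** With no cut stated, one of the two limited-efficacy measurements could be defined after the data are seen. Section 6.0 is specific elsewhere: a completed follow-up needs three named outcomes at four time points, and MSTS agreement means a difference below 10% in at least 70% of patients. Satisfaction has no comparable rule.

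**Working it through.** **Inputs from the documents.** 20 patients per group; two-sided 95% interval by the normal approximation; illustrative rates 0.50 and 0.70 (Section 6.0).

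**Assumption.** The survey gives a graded or summed score. The supplied text does not give its items, response scale or SD, so results are in SD units and shown as a range.

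**1. The plan's own figures.**
- One rate, widest case: 1.96 × √(0.25/20) = 0.219 (stated 0.22).
- Difference: 1.96 × √(0.50×0.50/20 + 0.70×0.30/20) = 1.96 × √0.023 = 0.297 (stated 0.30).

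Both reproduce. The plan's arithmetic is not in question.

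**2. Information kept by a cut, normal score.** Relative to the mean, a cut that classes a proportion p as satisfied keeps φ(z_p)² / [p(1−p)], where φ is the normal density and z_p the normal quantile.

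| Rate p | Kept | Lost | 20 patients act like |
|---|---|---|---|
| 0.50 | 0.637 | 36% | 12.7 |
| 0.60 | 0.622 | 38% | 12.4 |
| 0.70 | 0.576 | 42% | 11.5 |
| 0.80 | 0.490 | 51% | 9.8 |
| 0.90 | 0.342 | 66% | 6.8 |

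Under normality 36% is the smallest loss, and it grows as the rate moves away from one half.

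**3. The same comparison as interval width.**
- Score: 1.96 × √(2/20) = 0.62 SD; with the t quantile on 38 degrees of freedom, 0.64 SD.
- Rate at 0.50 and 0.70, each variance put on the SD scale by dividing by φ(z_p)²: 1.96 × √(0.0125/0.3989² + 0.0105/0.3477²) = 1.96 × √(0.0785 + 0.0869) = 0.80 SD.

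**4. Other score shapes.**
- Logistic score, median cut: kept 0.25 × π²/3 = 0.82 against the mean, or 3 × 0.25 = 0.75 against a rank analysis. The loss is 18-25%.
- Five ordered levels, against a rank analysis: kept 3p(1−p) / (1 − Σπ³), with π the level probabilities. Three illustrative distributions, each at its best cut:
  - (0.02, 0.05, 0.08, 0.35, 0.50), cut at the top level, keeps 0.90;
  - (0.10, 0.10, 0.30, 0.30, 0.20), cut at the top two, keeps 0.80;
  - (0.05, 0.10, 0.15, 0.40, 0.30), cut at the top two, keeps 0.70.

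  The loss is 10-30%. At a poor cut it is much larger: the first distribution cut at the top three levels (p = 0.93) keeps only 0.235.

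**5. A case with no gain.** Take five levels scored 1 to 5, with probabilities (0.05, 0.10, 0.35, 0.25, 0.25) in one group and (0.05, 0.10, 0.15, 0.45, 0.25) in the other. The rates in the top two levels are 0.50 and 0.70, and the whole shift sits at the cut.
- Means are 3.55 and 3.75, a difference of 0.20; variances are 1.2475 and 1.1875.
- Score: half-width 1.96 × √(2.435/20) = 0.68, so difference over half-width is 0.20/0.68 = 0.29.
- Rate: 0.20/0.297 = 0.67.

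Here the rate does better. The case is extreme, but it shows that the direction depends on the distribution.

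**The case against.** The strongest reply is that the premise is not documented. The survey was adapted by the research team, its response scale is not in the supplied text, and a satisfaction rate could come from one overall item with no score behind it. Appendix J may also hold a scoring rule. This stands, and it is why the precision argument is conditional. A cut found in Appendix J would settle the definition, but Section 6.0 would still plan no score analysis.

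A reader might infer that the plan throws away about a third of its information as a matter of fact. The documents do not support that: the figure needs a roughly normal score cut near its median, and the documents state neither.

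A reader might also infer a loss of power. Taking 0.50 against 0.70 as cuts of a normal score (a shift of 0.524 SD), exact power is 24% by chi-square, against 37% for a t-test on the score. That reading fails on three counts.
- The plan states no hypothesis test for satisfaction.
- It uses the two rates to illustrate interval width and does not present them as an expected satisfaction effect.
- The contrast shrinks under other choices. A logistic score gives the t-test about 31%. The plan's own type of interval excludes zero 32% of the time, though with a type I error of 7-8%.

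Two further limits stand. Controls have no mobile surveillance, so a score that mixes care and device items would not be comparable between groups. And the roughly 12 clinicians form one group, so none of the efficiency figures apply to them.

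Finally, a proportion is easy to read and natural for an acceptability aim. That is a reason to keep it, not to report it alone.

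**Conclusion.** The point holds in conditional form. Satisfaction is one of two limited-efficacy measurements, is planned only as a rate, and has no stated cut and no score analysis. The missing cut matters whatever the score's shape.

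The cost in precision rests on the survey giving a graded or summed score. If that score is roughly normal, the loss is at least 36%, and the interval at the plan's illustrative rates is about 0.80 SD where 0.62-0.64 SD was available. The loss exceeds 50% if about 80% or more of patients are satisfied. For coarse or heavier-tailed scores with a favourable cut it may be only 10-30%, and in some distributions the rate does better. Precision is the right measure here, because the plan frames limited efficacy by interval width.

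**What to change.** In Section 6.0, Limited Efficacy Testing:

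- Add the mean score per group on the care-satisfaction items that both groups can answer, and the between-group mean difference with a t-based 95% CI (Hodges-Lehmann if the scores are skewed). State its precision at 20 per group as ±0.64 SD.
- Report the device-use items in the mobile surveillance group only.
- Keep the satisfaction rate with its stated 0.22 and 0.30 precision, and fix the cut before the data are examined. If Appendix J already defines one, cite it.
- The clinician survey score may be reported descriptively, with no efficiency claim.

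The cost is a few sentences, with no new data, visits or patients. The small downside is that a mean on a modified form, for which the documents give no separate validation, is less immediate to read than a percentage. Keeping the rate beside it covers that.
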